The study uses a quasi-experimental design with pre-tests and post-tests for staff being trained. It provides a control group to directly compare the effects of the educational intervention upon the management of patients by measuring responses of patients before and after the staff is, or is not, trained. The Intervention Group (Clinic 1) and Control Group (Clinic 2) are non-randomly assigned. Both clinics agreed and looked forward to participating in the study, but one clinic had significant budget reduction that resulted in selection of the other clinic for the primary intervention. Ideally we would have used a cross-over design offering the intervention to the second site but the funding cycle for this proposal was reduced from 5 to 3 years and it is only feasible to offer one clinic the intervention. However, we intend to offer staff of the control site the palliative training at the end of the study period if the outcomes are shown to be beneficial. We will make a comparison of the two clinics at baseline to identify possible bias in the final analysis of data.

Following is a description of Study activities; at the end, the teaching intervention is described.

ITEMIZED RESEARCH ACTIVITIES: (See Timeline in Additional Documents)

The study is accomplished in 5 active phases with 3 desired outcomes: (A) staff will be able to use coping strategies as they integrate palliative skills with outpatient HIV care and treatment; (B) patients, specifically (YMSM), will be characterized in the era of successful ART with regard to mental health and quality of life; and (C) the curriculum, previously refined in international settings, will be re-adapted for use early in management of chronic illness in the US to engage and retain patients known to be difficult to keep in care.

PHASE 0:

Months 1-6

Usual study start-up activities including finalization of contracts, hiring of personnel, establishment of study offices, creation of the database and purchase of study materials.

PHASE 1: Patient Recruitment and Enrollment

Begins Month 7 of the study and continues through about Month 24.

A. STAFF: No staff are enrolled, taught or interviewed in the first Phase.

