A. STAFF: Initiation of educational process at Site #1. Directors of Site #1 have chosen to have a day-long educational session for All-STAFF to be introduced to CASA Study activity. The curriculum is attached in ADDITIONAL DOCUMENTS.

B. YMSM: Enrollment and data collection continue as described in Phase 1.

C. CURRICULUM - pre-finalized version to be delivered to staff at Site #1 as in-service education using usual pre- and post- training evaluation forms that reflect the content and will be used to further revise the curriculum.

PHASE 4: On-site Expert Coaching.

February 2015 through May to August 2016.

A. STAFF - The CASA Team (selected site-based staff) will meet bi-weekly with members of the trained external Expert Coaching Team to review progress with patients and with integration of palliative skills. These 2 teams will identify content for quarterly in-service education to be developed for all-staff of the clinic.

B. YMSM: Enrollment and data collection continue as described in Phase 1.

C. CURRICULUM: Final revisions of curriculum based upon staff feedback. This curriculum will be put together in manual form for the end of the study.

PHASE 5 - Post-educational interviews

Approximate Months 28 - 30

A. STAFF - Up to 25 staff members per clinic will be asked to participate in in-depth structured interviews to obtain reports of their experiences with, or without, CASA and its implementation, including their perceptions of its impact on their own behaviors and clinic practice. These staff interviews will include members of the trained CASA Team as well as other members of the clinic staff potentially impacted by the training. Up to 25 staff at each clinic will be recruited, consented and complete pre- and post-intervention surveys, in months 28-30. Participation of staff will be a voluntary process although staff will be reimbursed a token amount for completing an interview. A separate consent form will be developed. Details of these interviews will be developed following the MID-STUDY data review and this information will be uploaded in CICERO once the content is determined and prior to these interviews taking place.

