This is a longitudinal, descriptive study evaluating the impact of an educational training for outpatient clinic staff on patient outcomes cared for by the trained staff members. The analyses are complex: 1) there are 2 target groups (staff and patients); and 2) the intervention is offered in 3 stages (teaching; coaching; all-staff education); and it is a pre-post comparison of the impact of a training intervention upon patients cared for by trained staff using 1 site as the control for the other.

The data collected is psycho-social, meaning both psychological and sociological, reflecting graded rather than dichotomous, or Yes-No responses. This means that multiple comparisons are being made. This large array of data requires mathematical modeling to describe true associations and accurate interpretation of the data. This is explained in detail below.

For PATIENTS quantitative results (survey responses) are supplemented by data extracted from the clinical electronic medical record (EMR) and by qualitative interviews with selected participants from each of the 2 target groups.

Addressing AIM 1: STAFF:

QUANTITATIVE: We will use data from Staff-Baseline and Staff-Follow-up surveys at both sites. We will enroll up to 80 STAFF members between the 2 sites. An array of descriptive and graphical techniques will be performed to characterize the distribution of the variables at each point in time as well as aggregate change in work-related stress, or burnout from Baseline (B) to Follow-up (F). Point estimates with confidence intervals will be used to estimate population values. Comparisons of data from participants in the Intervention and Control groups at Baseline (B) will identify potential heterogeneities between sites with regard to the distribution of staff background characteristics that might be related to stress or burnout (e.g., staff's clinic role/position -- physician, nurse, outreach worker, substance abuse counselor, etc.).

Between-group comparisons at B and F will be made with chi-square, t-tests (Fisher's exact as appropriate) and comparisons of change across time will be assessed by paired Student's t-test or paired Wilcoxon test. Post-hoc power calculations will be performed to determine if we have adequate statistical power for further testing.

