Several unadjusted and adjusted Cox Proportional Hazard regression models will be estimated for comparing survival curves between Site 1 and Site 2 including models that allow for time-varying correlates [e.g., Cox-Aalen (97)]. Evidence of a short-term intervention effect on attendance (retention in care) will be made by comparing survival curves at both sites from 8 months (prior to the baseline assessment) to 16 months following the initiation of the intervention training at Site 1. Descriptive analyses and identification of sample heterogeneities and potential sources of bias. Summary statistics and graphical displays will present characteristics of study participants in each intervention arm as reported at B, F1, and F2, as well as to describe aggregate change of time-varying measures over three time periods: B to F1 (short-term gains), B to F2 (longer-term), F1 to F3 (maintenance).

BIAS: Analyses will be conducted to identify potential sources of bias that may require statistical redress in multivariate analyses. Characteristics of participants in the experimental arm at B will be compared to those of patients in the Control group to identify potential heterogeneities between samples. Given the nonrandom assignment of patients to study arm, it will be necessary to compare characteristics of participants in the study arms at B to identify potential heterogeneities between sites with regard to the distributions of patient or other background characteristics that research suggests might be related to patient outcome(s). Characteristics of participants at B will be compared on the basis of their level of study completion (only B, B+F1, or B+F1+F2) to assess attrition and identify its potential correlates. Between-group comparisons within a single interview will be made with chi-square, t-tests (Fisher's exact as appropriate) or one-way ANOVA with F-tests of significance; and comparisons of change across time assessed by paired Student's t-test or paired Wilcoxon test. Concordance between measures at different times will be assessed using correlation coefficients: Pearson or Kendall tau/Spearman. Probit modeling will be used to determine whether specific patient characteristics, stressors, and/or modifiers are associated with attrition.(119) Propensity analyses (93) will be conducted to calculate terms to control for potential unbalance between intervention arms (see "Propensity Scores" below) will be used.

Addressing Aim 3. CURRICULUM:

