Descriptive analyses of the training evaluation forms (to be developed following refinement of the curriculum and submitted to the IRB before being used with STAFF) completed by the teaching team or instructors, expert coaches, and HIV clinic staff including administrative staff during all 3 levels of the CASA training including quarterly all-staff educational sessions will be used to evaluate the training. This analysis will 1) confirm that topics and issues intended to be taught were presented including cultural issues; 2) document both consistency and completeness of the training; 3) identify unanticipated issues raised during the training; and 4) identify aspects of the training that need revision or expansion. These descriptive analyses represent what Cook, Cook and Mark (26) refer to as the "take" of the intervention, or how successful the training is at accomplishing what it intends. Participant insights will be used to suggest training revisions to improve the "reach", or scope of the training, success of implementation and overall effectiveness of the training for other settings. The "reach" describes both breadth and depth of the impact of the training. Attendance logs will document that all members of the team received the training.

We will use the RE-AIM framework [62] in analyzing the acceptability, feasibility, and impact of the CASA intervention. The RE-AIM framework focuses on the content and outcome of a training and guides examination of the clinics including the social, cultural, and care needs of the YMSM. The analysis focuses on essential training elements that foster implementation and sustainability of the training incorporating staff and patient perspectives.

LONGITUDINAL DATA ANALYSIS:

The third analysis is longitudinal and will examine trends of change in study outcomes that will describe potential correlates/mediators of change, as well as comparisons of change in study outcomes for both populations (STAFF and PATIENTS) and potential correlates between study arms. Thus we are able to determine training effect and analyze maintenance and sustainability of intervention effects. Assumptions will be checked with non-parametric alternatives. Appropriate multiple testing techniques (i.e., Bonferroni) will be applied as needed. Analyses will be conducted using SAS 9.3 or IBM SPSS Statistics v20.

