Longitudinal analysis of the training effect and its long-term maintenance/sustainability. We will describe trends over time (short-term [baseline to first follow-up], longer-term [baseline to second follow-up], and maintenance [follow-up 1 to follow-up 2]) in the remaining study outcomes and potential correlates, using Laird and Ware's longitudinal analysis techniques.(162) This involves model choice and potentially model averaging. A best model will be chosen based on the Akaike information criterion.34 Model averaging techniques might prove useful given "a priori" information is available about factors likely to be associated with improved outcome. Longitudinal techniques will be used to identify relationships among changes over time, baseline characteristics and behaviors at follow-ups 1 and 2.

Multiple regressions will be used to estimate models predicting residualized change (short-and long-term) scores (27) for study outcomes, including potentially relevant covariates (characteristics and stressors) plus a term noting the intervention arm in which the patient participated. Next, to test if an effect noted for the Intervention Arm from the 1st model is accounted for by the impact of the intervention on the mediators, these models for outcomes will be re-estimated including residualized change scores for the mediators.

For both sets of analyses:

- a term will be included to balance the arms (based on propensity score matching);
- assumptions will be checked; non-parametric alternatives and transformations considered; and, if needed, appropriate terms added to control for biases associated with failures of randomization and/or attrition;
- heterogeneity of intervention effect will be examined using statistical modeling to determine the interaction between the intervention and other covariates. [Examining relationships between changes in outcomes and various factors (e.g. demographics, SES, social support) will determine factors that define heterogeneities of intervention effects. Statistical interactions will be examined using graphical displays and statistical tests of interaction]

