GROUP 2 of STAFF = All STAFF at each of 2 HIV sites will be asked to complete a BASELINE and FOLLOW-UP survey. The STAFF will be asked to complete a survey about work-related stress BEFORE and AFTER the teaching intervention. This process was previously approved by the IRB but only partial survey content was uploaded. This survey will be completed following a consent process and before 1/30/2015.
The CONTENT of the survey includes the AIDS Stress scale and the Burn-out Inventory previously up-loaded in CICERO. The survey consists of 12 items plus the Professional Quality of Life* instrument. The latter is a measure of compassion satisfaction, secondary traumatic stress and burn-out. The other 12 items ask for demographic and educational background as well as time in HIV care delivery and the Burn-out Inventory. The total time to complete this survey would be a maximum of 15 minutes and each staff person at the intervention site would be asked to complete it 2 times (Baseline - January or February, 2015 and Follow-up – April or May, 2016).

2) PATIENTS: HIV positive young men who have sex with men (YMSM) ages 18-35 year who attend either of 2 outpatient HIV clinics on the UMB-UMMC campus. The consent process begins with appropriate training for those involved in research who will be trained to assist the Principal Investigators in screening for eligibility and conducting the consent process for patients identified above who are eligible for this study.
Once PATIENTS are identified by staff of the clinic and the patients primary care provider has indicated that it is appropriate to contact the patient, a member of the Research Team will meet with the patient to describe the study and to answer questions. The patient will be given the opportunity to take the consent form home to review with someone else and when all of his questions have been addressed he will be asked to sign the consent form and will be given a copy for himself. The study staff will review with the enrollee procedures for contacting study staff and will obtain from him mechanisms for making contact should the telephone number given not be functional.

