For STAFF to be enrolled, the same attention to privacy and confidentiality will be maintained. This is an in-service educational intervention for staff where the INTERVENTION begins 1/2015 and is completed approximately 18 months later. The reason for completing the Informed Consent Process is that STAFF are being asked to complete a de-identified pre- and post-educational survey related to work-related stress in caring for persons living with HIV disease. All STAFF have already been aware of the CASA study being conducted at the site and have attended an introductory lecture about the study. The site management staff will alert them about the survey and they will have the opportunity to refuse to complete the survey without having any impact on their employment or in their attendance at the all staff training sessions.

The selected PATIENTS or STAFF who will be asked to participate in qualitative interviews will complete a separate process with regard to these interviews and their questions will be answered. They will be advised again that their participation is voluntary.

3 * Confirm that the consent process will explain the following:

- The activities involve research.
- The procedures to be performed.
- That participation is voluntary.
- The name and contact information for the investigator.

Yes No

4 * Describe who will obtain Informed Consent:

A trained member of the Research Team or the UMB Principle Investigator will obtain the consent for each enrollee in the study. Members of the Research Team will be coordinated and supervised by the Program Manager and will have direct access to [name].

In this case the training includes CITI training, HIPAA training, training by [name] the Co-Principle Investigator for this study and supervision by [name] and the Program Manager. There will be direct on-site observation of the consent process until we are assured that members of the Research Team are comfortable and competent in this role.

Research Team members trained to enroll PATIENTS will receive further training in enrollment of STAFF and the need to assure that their participation is voluntary.

5 * If obtaining consent from a legally authorized representative (LAR), describe how you will confirm that the individual is the LAR and can provide legally effective informed consent. (Answer "N/A" if not obtaining consent from LARs)

N/A

6 * Describe the setting for consent:

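### Change from follow-up 1 to follow-up 2 is labelled maintenance, but for most Site 1 patients that interval lies inside the intervention, and staff have no such contrast

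*Combined protocol and SAP*

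**What the plan says.** **The claim.** Sample Size and Data Analysis, question 2, LONGITUDINAL DATA ANALYSIS, refers to change in both staff and patients and concludes: "Thus we are able to determine training effect and analyze maintenance and sustainability of intervention effects". The next paragraph defines the patient contrast as "maintenance [follow-up 1 to follow-up 2". The SURVIVAL ANALYSIS paragraph instead gives "F1 to F3 (maintenance"; no third follow-up is planned anywhere.

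**The intervention.** The opening of DATA ANALYSIS states that "the intervention is offered in 3 stages (teaching; coaching; all-staff education". Phase 4 of the research design dates coaching "February 2015 through May to August 2016". The Informed Consent Process section agrees with this: "INTERVENTION begins 1/2015 and is completed approximately 18 months later".

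**Patients.** Phase 1 enrolment "Begins Month 7 of the study and continues through about Month 24". Surveys are about 6 months apart in Phase 1 and 4–6 months apart in Study Procedures, question 3. Study Procedures, question 1, allows up to 18 months for the two follow-ups.

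**Staff.** There is one baseline and one follow-up survey. The Informed Consent Process section puts the follow-up at the intervention site in "April or May, 2016".

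**Medical records.** Surveys/Questionnaires has clinic data coded monthly from 6 months before accrual to 18 months of follow-up.

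**The concern.** Maintenance of an effect is what remains once the intervention has stopped. The plan defines it by survey order and does not tie it to the end of coaching. If the expert team is still working with Site 1 staff at F2, a flat or rising F1–F2 trend shows change under continuing support. Reported under the plan's label, it would be read as a durable effect. This matters for a proof-of-principle study whose curriculum is to be published for replication: a clinic adopting it would want to know whether gains outlast the coaching. Staff have a single follow-up, so the claim extended to them has no contrast behind it.

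**Working it through.** **Calendar.** Phase 2 equates Month 13 with November 2014, so Month 1 is November 2013. The funding dates in Study Procedures, question 4, would make Month 1 October 2013. I used both.

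The one timing figure in the plan that can be tested reproduces: data collection from April 2014 to an intervention in January 2015 is 9 months, as Study Procedures, question 1, states.

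| | Month 1 = Nov 2013 | Month 1 = Oct 2013 |
|---|---|---|
| Training starts, Jan 2015 | 15 | 16 |
| Coaching starts, Feb 2015 | 16 | 17 |
| Coaching ends, May 2016 | 31 | 32 |
| Coaching ends, Aug 2016 | 34 | 35 |

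**Rule.** Let entry month e run from 7 to 24 (18 months, even entry assumed) and let s be the survey spacing, so F1 = e + s and F2 = e + 2s. A survey counts as after coaching only if its month is later than the last coaching month.

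**Spacing of 6 months, entry months out of 18:**

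| Coaching ends | F1 before training | F1 in the first training month | F1 and F2 both within coaching | F2 after coaching |
|---|---|---|---|---|
| Month 31 (Nov anchor) | 2 (e = 7–8) | 1 (e = 9) | 10 (e = 10–19) | 5 (e = 20–24) |
| Month 34 (Nov anchor) | 2 (e = 7–8) | 1 (e = 9) | 13 (e = 10–22) | 2 (e = 23–24) |
| Month 32 (Oct anchor) | 3 (e = 7–9) | 1 (e = 10) | 10 (e = 11–20) | 4 (e = 21–24) |
| Month 35 (Oct anchor) | 3 (e = 7–9) | 1 (e = 10) | 13 (e = 11–23) | 1 (e = 24) |

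So F1–F2 lies wholly within coaching for 10–13 of 18 entry months. For 2–3 of 18 it spans the start of training.

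**Spacing of 4 months.** F2 after coaching needs e + 8 > end. That gives 1 of 18 if coaching ends at Month 31 (e = 24) and 0 for the other three end dates. Over 4–6 months the range is therefore 0–5 of 18 (0–28%), or at most 5/18 × 102 ≈ 28 of the 102 Site 1 patients before attrition.

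**Full 18 months used.** F2 after coaching needs e + 18 > end: 11 of 18 (end 31), 10 (end 32), 8 (end 34) and 7 (end 35). The range is 7–11 of 18 (39–61%). This is generous: with a November 2013 anchor, an 18-month visit for e = 24 falls in April 2017, after the study ends in March 2017.

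**Medical-record outcomes.** Coding runs to e + 18, so the same 7–11 of 18 entry months reach past coaching.

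**Sensitivity to the end date.** If coaching stopped at the very start of May 2016, the 6-month figure would rise from 5 to 6 of 18.

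**Staff.** A follow-up in April or May 2016 falls 0 to 4 months before coaching ends. Two surveys give one change score and no second interval.

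**The case against.** Several points on the other side are fair.

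- **One survey during coaching and one after can inform on maintenance.** A reader might infer from the calendar that no maintenance contrast is possible because no patient has both follow-ups after coaching (the latest F1 at 6-month spacing is Month 30). That test is too strict; the relevant count is F2 after coaching. Such patients exist, but the plan neither identifies nor separates them.
- **Medical-record outcomes.** Attendance and viral suppression are abstracted monthly to 18 months. A reader might infer that the design holds no post-coaching information at all. It holds some for these outcomes.
- **RE-AIM and interviews.** The plan also addresses sustainability qualitatively, and the interview guides are dated January 2017. That is untouched by this point, but it does not justify the F1–F2 label.
- **Dates are approximate.** Enrolment ends at about Month 24, continues until 102 per site, and carries on in Phase 4. A patient consent form is dated March 2016, and staff survey files carry dates in July 2016 and January 2017. Later patient entry or staff data cannot be excluded. Patients entering after Month 24 would have their baseline survey after training began.
- **Staff contrast never specified.** Maintenance is defined only through two follow-ups, and the staff analysis is already limited to subgroup description. This supports removing staff from the claim.
- **Narrow meaning of intervention.** If only the early-2015 teaching counted, F1–F2 would follow it for many patients. The plan's own three-stage description rules this out.
- **Importance.** Maintenance is not in the specific aims or the hypothesis, does not drive the sample size, and is introduced as describing trends. This lowers the severity.

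**Conclusion.** The concern holds in limited form. F1–F2 does not measure maintenance for most Site 1 patients: at 6-month spacing it lies wholly within coaching for 10–13 of 18 entry months, and F1 precedes training for 2–3. F2 falls after coaching for 0–5 of 18 at the stated 4–6-month spacing, or 7–11 of 18 if every patient uses the full 18 months. No staff maintenance contrast exists. The limit applies chiefly to survey outcomes and staff.

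The counts rest on even entry over Months 7–24, coaching ending within the stated May–August 2016 range, and a start in October or November 2013.

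A reader might go on to treat the whole F1–F2 interval as change during continued coaching. The documents do not support that either: Site 2 is never coached, some Site 1 patients have F1 before training, and some have F2 after coaching.

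Severity is minor to moderate. No primary estimate or power figure changes, but a stated conclusion does.

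**What to change.** 1. In LONGITUDINAL DATA ANALYSIS, call the contrast *change from follow-up 1 to follow-up 2*, and state that it is not interpreted as maintenance or sustainability. Correct the F1-to-F3 entry under SURVIVAL ANALYSIS to match.
2. Remove staff from the maintenance claim.
3. If sustainability is kept, classify each patient's observations by calendar time: before training, during the intervention, and after the last coaching session. Apply the same calendar periods at Site 2. Base the claim only on post-coaching observations, mainly medical-record attendance and viral load, obtained while the two clinics were still separate. Recruitment and Informed Consent Process both say the clinics were combined but give no date, so that date must be recorded. If no observations remain, drop the claim.

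**Cost.** A wording change plus, if sustainability is kept, a classification of data already being abstracted; no new data collection. The downside is a weaker stated claim, or sustainability judged only on late entrants, who mostly have no baseline survey from before training.

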Sample size calculations were made for logistic regressions predicting the likelihood of patients reporting viral suppression which indicates control of their disease (meaning that the patient is actually taking ART as prescribed). This is based upon the following assumptions: (1) improvement of 10% in patients reporting viral suppression by Follow-up #2 Survey among patients at Site 1 (experimental); (2) $1 - \beta = 0.8$; (3) $\alpha = 0.05$; and (4) $deff = 2.2$.

These analyses estimate the need for a total sample size of 170 (85 per site) at study end. Allowing for 20% attrition from Baseline to Follow-up 2 it will be necessary for us to accrue a total of 204 patients (102 at each site) in order to have a sufficient number of patients completing all 3 Patient Surveys. This number is higher than the number of patients we estimated to be required for the two-sample comparison of survivor functions using Cox Proportional Hazard regressions ($n=140$), (176) allowing for attrition. This sample size provides adequate power for the proposed longitudinal regression models. Based upon analyses made with N-Query Advisor 7.0 software 44 assuming $\alpha = 0.05$ and power $(1 - \beta) = 0.8$, the 170 cases completing Baseline, Follow-up 1 & Follow-up 2 will allow us to identify "small to medium" effects for the total model ($R^2 = 0.063$) and individual coefficients as well as a "medium" effect for up to each of 15 co-variates on R^2 (as small as 0.055) as outlined in Cohen (29).

The proposed sample size will allow us to estimate models including: a) a dummy variable noting the intervention arm, b) a term to correct for attrition bias, c) the baseline counterpart of the dependent (patient outcome) variable, and, d) a set of up to 12 relevant co-variates.

ENSURING ELIGIBLE PATIENTS:

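### The arm model for continuous patient outcomes uses residualized change scores with no baseline outcome named, the sample-size section lists that baseline as a term, and the plan does not reconcile the two

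*Combined protocol and SAP*

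**What the plan says.** The arm regression for patient outcomes is in Sample Size and Data Analysis, item 2, under the longitudinal analysis of the training effect: "Multiple regressions will be used to estimate models predicting residualized change (short-and long-term) scores (27) for study outcomes, including potentially relevant covariates (characteristics and stressors". Arm enters the same model as a term of its own. A balancing term based on propensity scores is added, and further correction terms only if needed. The same section then tests mediation: "these models for outcomes will be re-estimated including residualized change scores for the mediators". It does not say how any residualized score is computed. It cites a source that cannot be checked here.

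Item 1 of the same section, under the sample size, describes the models that the sample supports. They contain an arm dummy, an attrition term, "the baseline counterpart of the dependent (patient outcome) variable" and "a set of up to 12 relevant co-variates", so 1 + 1 + 1 + 12 = 15 terms.

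The study design section says: "The Intervention Group (Clinic 1) and Control Group (Clinic 2) are non-randomly assigned". The paragraph on bias adds: "Given the nonrandom assignment of patients to study arm, it will be necessary to compare characteristics of participants in the study arms at B". The propensity score section builds the score from site-related covariates and every covariate of the final model.

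**The concern.** A residualized change score is usually the residual of follow-up after regression on baseline. The mediators' scores enter as regressors, so they must be computed variables. That makes a separately formed score the natural reading for the outcomes too. If the first regression omits arm and covariates, its slope absorbs the part of their effects that is correlated with baseline. A second regression without baseline cannot give that part back. With one clinic per arm and no randomisation, a baseline difference between arms is possible, and the arm coefficient then differs from the baseline-adjusted difference. At stake is the estimated training effect on outcomes such as quality of life and self-esteem, and the test of whether mediators account for it.

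**Working it through.** The plan gives no figure for this analysis, so there is none to reproduce. Only the 85 patients per site come from the documents. The clinic difference, slopes and correlations below are assumptions.

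**1. Outcome model.** Let F = follow-up, B = baseline, A = arm, X = covariate, and F = τA + βB + γX + e.

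- First step, F on B alone: slope = β + τc + γk, with c = Cov(A,B)/Var(B) and k = Cov(X,B)/Var(B).
- Residual = τA + γX − (τc + γk)B + e, apart from a constant.
- Second step on A and X without B: arm coefficient = τ − (τc + γk)δ, where δ is the clinic difference in B adjusted for X.
- Second step with B added: subtracting a multiple of B changes only B's own coefficient, so the arm coefficient is exactly that of the one-step model.

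**2. Numbers.** Assume B has SD 1 within clinic and clinic difference d. Assume X is standardised, balanced between clinics and correlated 0.5 with B. The residual variance is 0.6. Then Var(B) = 1 + d²/4, c = (d/4)/Var(B), k = 0.5/Var(B) and δ = d.

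Example with d = 0.3, τ = 0.40, γ = 0.3: 0.40 − (0.40 × 0.0733 + 0.3 × 0.489) × 0.3 = 0.40 − 0.176 × 0.3 = 0.347.

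| d | Var(B) | c | k | γ = 0 | γ = 0.3 | γ = −0.3 |
|---|---|---|---|---|---|---|
| 0.3, τ = 0.40 | 1.0225 | 0.0733 | 0.489 | 0.391 | 0.347 | 0.435 |
| 0.5, τ = 0.40 | 1.0625 | 0.1176 | 0.471 | 0.376 | 0.306 | 0.447 |
| 0.3, τ = 0 | 1.0225 | 0.0733 | 0.489 | 0 | −0.044 | +0.044 |
| 0.5, τ = 0 | 1.0625 | 0.1176 | 0.471 | 0 | −0.071 | +0.071 |

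With γ = 0 the factor is 1 − cd: 0.978 and 0.941, a loss of about 2% and 6%. With d = 0 every bias is zero.

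Simulation at 85 per site agrees. For γ = 0.3 the mean is 0.344 to 0.348 at d = 0.3 and 0.308 to 0.312 at d = 0.5. For γ = −0.3 it is about 0.43 to 0.44. The one-step model gives 0.40, or 0.00 under no effect. For γ = 0.3, power is 80% against 90% one-step at d = 0.3, and 72% against 90% at d = 0.5. For γ = −0.3, power does not fall.

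**3. Type I error.** The standard error is about √(0.6 × 4/170) = 0.119. The null shifts are 0.044/0.119 = 0.37 and 0.071/0.119 = 0.60 standard errors. Two-sided rejection is Φ(−1.59) + Φ(−2.33) = 6.6% and Φ(−1.36) + Φ(−2.56) = 9.2%. Simulation with 1,500 replicates gave 5.3% and 8.7%.

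**4. Propensity term.** For γ = 0.3, adding a score that excludes baseline leaves the estimates at 0.344 and 0.312. A score that includes baseline gives 0.399 and 0.406.

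**5. Mediation.** Let R be the mediator's pooled residual, so that its follow-up value is M1 = R + s·M0 plus a constant, where M0 is its baseline. If the outcome depends on M1 with coefficient θ and the direct arm effect is zero, entering R without M0 leaves θ·s·M0 in the error. The arm term then picks up roughly θ·s·d, with d now the clinic difference in M0. With θ = 0.4 and s = 0.5 (assumed), this is 0.4 × 0.5 × 0.3 = 0.06 and 0.4 × 0.5 × 0.5 = 0.10. Simulations that kept the outcome's baseline in the model gave biases of 0.05 to 0.10 and false-positive rates of about 8 to 13%. Adding M0 brought the rate back to about 5%.

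**The case against.** The strongest reply is that the sample-size section already lists the outcome's baseline, and leaving a term out of a later paragraph does not contradict it. With that term the arm estimate is the one-step estimate, and by its own rule the propensity score then contains baseline too. This stands. A reader might infer that the plan excludes baseline and that the arm estimate is therefore biased. The documents do not support that. They leave the model open.

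Other stronger readings also fail:

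- **Type I error is inflated in general.** It is not. Null bias needs both a clinic difference at baseline and a covariate that is correlated with baseline and predicts follow-up beyond it.
- **The training effect is always understated.** The sign follows τc + γk. With a negative covariate effect the estimate rises to about 0.43 to 0.45.
- **The plan expects the clinics to differ at baseline.** It looks for possible differences, and the propensity section anticipates strong overlap between the arms.
- **This is the only analysis of these outcomes.** Laird-Ware longitudinal models are also named. Viral suppression, on which the sample size rests, is analysed by logistic and GEE models that this point does not touch.

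The reply does not settle two things. Nothing says that the sample-size list governs the analysis paragraph. And that list covers the baseline of the dependent variable only, not that of a mediator.

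**Conclusion.** The point holds in a conditional form. The analysis paragraph and the sample-size section describe different models and are not reconciled. On the literal reading (pooled residual, no baseline in the second step), a baseline difference of 0.3 to 0.5 SD between clinics costs about 2 to 6% of the effect when covariates add nothing beyond baseline. With a covariate correlated 0.5 with baseline and an effect of ±0.3, a true 0.40 SD is estimated as about 0.31 to 0.35 or 0.43 to 0.45, and type I error is about 6 to 9%. These sizes rest on assumed inputs. If the clinics match at baseline, or if the listed baseline term is kept, the bias in the outcome model is zero. The mediation step stays exposed even then if the clinics differ on the mediator at baseline. The point deserves correction because the plan can be followed as written to a wrong arm effect, while the data that prevent this are already collected.

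**What to change.** In the longitudinal analysis section, replace the residualized score as dependent variable by the follow-up score itself (first or second follow-up). Fit it in one step on its baseline value, arm, covariates and the balancing term, consistent with the model listed under the sample size. State that the baseline outcome is in the propensity model. In the mediation step, enter each mediator's follow-up value together with its own baseline value instead of a residualized score.

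The cost is wording, one degree of freedom for the outcome's baseline (already among the 15 terms) and one more per mediator. No new data are needed. The change does not address unmeasured differences between two non-randomised clinics.
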